### Methods and Timing for Assessing, Recording, and Analyzing Safety Parameters

#### Notification of Unplanned Healthcare Utilizations and Deaths

Unplanned healthcare utilization (intensive care unit transfers, emergency department visits and/or hospitalizations) and deaths are monitored throughout all study phases for each participant. Both the study coordinator and the data manager have access to a study patient panel in the electronic health record. As such, any time a participant is admitted to the VUMC Emergency Room, VUMC Inpatient Services, or the participant's medical record is updated to indicate death, the coordinator and data manager receive a notification. To determine if a participant had an unplanned healthcare utilization at an outside hospital (OSH), the participants are asked at each follow-up time point if they have been to an emergency room or had an inpatient stay, and if so, at what facility. The study coordinator and data manager are responsible for requesting medical records from OSHs (and SNFs) relevant to the utilization.

#### Review of Unplanned Healthcare Utilizations and Deaths

Any unplanned healthcare utilization (e.g., hospitalization, ER visit) or unplanned death (e.g., patient not receiving hospice care) is reviewed to determine if it was an adverse event that was serious, related to the study, and unexpected (SUSAR). Once all necessary records have been obtained and collated by the study coordinator, the case is assigned to a physician co-investigator for review. The adjudicator uses an established methodology to determine the presence of serious medication errors and will determine whether the unplanned healthcare utilization is related to medication withdrawal (i.e., ADWE) using the 10-question Drug Withdrawal Probability Scale, a scale based on the Naranjo algorithm, which is a validated scoring system to assess causality of adverse drug events. ADWE will be coded as definite (>8), probable (5-8), possible (1-4), and doubtful (<1). For all ADWEs, the clinician-adjudicator will then determine whether it was avoidable by any change in management. After review by the clinician-adjudicator, the case is sent to the Principal Investigator to review. Both the PI and a co-investigator review to determine if the event was unexpected and/or study related. Should the event be determined as SUSAR (serious, unexpected, and study related) it will be reported as such to the DSMB and IRB as outlined below.

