## SAFETY MONITORING AND ASSESSMENTS

We have established a system to report and track adverse events (AEs) including adverse drug withdrawal events (ADWEs), serious adverse events (SAEs), and Suspected Unexpected Serious Adverse Reaction (SUSARs). In this study, an SAE is defined as an unplanned hospitalization or death, and an AE is defined as an emergency room visit that does not result in hospitalization. A SUSAR is an SAE that is suspected to be secondary to the drug withdrawal and is unexpected. Study personnel will monitor the safety of subjects and follow them until the event resolves or is explained.

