### Serious Adverse Events and Reporting Procedures

To ensure proper and timely reporting of adverse events, the following communication plan is utilized. The project coordinator is responsible for reporting adverse events to the safety officer and the IRB in a timely manner and in accordance with the IRB's guidelines. Our procedures are as follows:

1. IRB: PI will notify the IRB of any Serious, Unexpected, Study Related Adverse Event within 7 days of PI notification of the event. Any noncompliance with the IRB approved protocol that increases the risk or affects the patient's rights, safety, or welfare also need to be reported within one week. At the time of the IRB annual continuing review, the IRB receives copies of the reports prepared for the safety officer. Reports that identify a new risk or a change in the risk benefit ratio must be submitted to the IRB within 10 days of receipt by the PI.
2. Safety Officer: PI will notify the safety officer of any SAEs regardless of study-relatedness. Additionally, the safety officer will receive semi-annual reports summarizing all SAEs and AEs.

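### The withdrawal-causality scale is named only for unplanned utilization: deaths are not named, hospice deaths appear to skip the review, and withdrawal events managed in the facility have no stated route to it

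*Combined protocol and SAP*

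**What the plan says.** Under *Safety Monitoring and Assessments*, the system is said to track "adverse events (AEs) including adverse drug withdrawal events (ADWEs"), together with SAEs (the serious category) and SUSARs. On the non-serious side, "an AE is defined as an emergency room visit that does not result in hospitalization". The serious category takes in deaths and hospitalizations that were not planned. The third category rests on suspicion of withdrawal: "A SUSAR is an SAE that is suspected to be secondary to the drug withdrawal and is unexpected".

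Under *Review of Unplanned Healthcare Utilizations and Deaths*, any unplanned utilization or "unplanned death (e.g., patient not receiving hospice care) is reviewed to determine if it was an adverse event". A physician co-investigator adjudicates and "will determine whether the unplanned healthcare utilization is related to medication withdrawal (i.e., ADWE") with the 10-question Drug Withdrawal Probability Scale. The codes are definite (>8), probable (5-8), possible (1-4) and doubtful (<1). The principal investigator (PI) and a co-investigator then judge whether the event was unexpected or study related.

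Under *Notification of Unplanned Healthcare Utilizations and Deaths*, deaths are monitored in all phases. For outside hospitals, "participants are asked at each follow-up time point if they have been to an emergency room or had an inpatient stay".

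Under *Serious Adverse Events and Reporting Procedures*, "PI will notify the safety officer of any SAEs regardless of study-relatedness". The duty towards the institutional review board is narrower: "PI will notify the IRB of any Serious, Unexpected, Study Related Adverse Event within 7 days of PI notification of the event". The *Safety Officer* section adds a six-monthly list of adverse events (AEs) and SAEs, classed by severity and by likely relation to study procedures.

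The *Précis* presents closer monitoring for withdrawal symptoms as the leading potential advantage of an assisted-living setting. *Approach to potential risks* lists weekly follow-up as a safeguard for detecting ADWEs.

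**The concern.** The plan stops or reduces drugs in frail residents and promises close attention to withdrawal. The one procedure that scores withdrawal causality starts from an emergency visit, a hospitalization or an unplanned death. A withdrawal reaction that staff notice and manage on the unit is what in-facility monitoring should detect, yet the plan does not say how it reaches the adjudicator. Hospice residents are deliberately eligible (*Background and Significance*) and made up 12 of the 41 residents at the first site when the project began (*Study Setting*), but their deaths appear to be left out of the review.

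ADWEs are a tracked safety result and not a listed outcome, so no planned test depends on them. What is at stake is the meaning of the ADWE count. The pilot is meant to prepare a multi-center trial, and a low count could reflect the entry rule and be mistaken for evidence of safe deprescribing.

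**Working it through.** The documents give no ADWE count, rate or expected number, so there is no figure to reproduce. The check traces each kind of event through the stated steps.

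| Event | Enters the review? | Scale named for it? | Other stated handling |
|---|---|---|---|
| Emergency visit or unplanned hospitalization, hospice resident or not | Yes | Yes | PI and co-investigator judgement; safety officer |
| Death outside hospice | Yes | No | SUSAR judgement, which is tied to drug withdrawal; safety officer |
| Death in hospice | Apparently not | No | If counted as an SAE: safety officer and general relatedness class |
| Withdrawal event managed in the facility | No stated route | No | None stated; may appear in fall or behavioral-symptom counts |

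**Is there another route for the last row?**
- The follow-up question covers emergency visits and inpatient stays only.
- The abstraction in *Secondary Outcomes* tallies behavioral episodes, falls and utilization. It does not record whether an event followed a drug change.
- Table 1 has no ADWE row.
- In *Pre-Review*, deprescribing actions 2, 4 and 6 (3 of 6) specify monitoring. No section says where a positive finding is recorded.
- Weekly follow-up is mentioned once, with no form, threshold or link to the adjudicator. *Interventions and Duration*, *Study Procedures* and Table 1 describe enrollment and 30, 60 and 90 days.

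**Direction.** Let T be the true number of ADWEs, s the share that the entry rule admits, and F the events wrongly coded as ADWEs. Then

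observed tally = T × s + F.

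All three are assumptions, used only to show direction:
- T = 4, F = 0: s = 1, 0.75, 0.5 and 0.25 give 4, 3, 2 and 1. With F = 0 the tally never exceeds T.
- T = 4, F = 2: the same values of s give 6, 5, 4 and 3. At s = 0.75 the tally is 4 × 0.75 + 2 = 5, above the true 4.

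The entry rule acts only through s, so by itself it can only lower the count or leave it unchanged. F need not be zero, because the lowest code is doubtful and no cut-off is given for a counted ADWE.

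**The case against.** The strongest reply is that the plan chose a scope. If an ADWE means utilization related to withdrawal, as the scale sentence can be read, then tracking AEs including ADWEs fits an AE definition based on emergency visits. A reader might infer that the safety section contradicts itself; the documents do not force that reading. The breadth of that definition still matters, because the *Précis* and the weekly follow-up statement speak of withdrawal more broadly.

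Other stronger readings also go too far:

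- *That deaths get no withdrawal judgement.* Deaths outside hospice enter the review and are judged for SUSAR status, which is defined by drug withdrawal. Only the scale is not named for them. Leaving out hospice deaths is an inference from an example. Hospice residents with an emergency visit or hospitalization still enter, and hospice deaths, if SAEs, still go to the safety officer.
- *That the reported ADWE tally must be too low.* This holds for the entry rule alone and not for the net tally.
- *That facility-managed events escape the 7-day notice to the institutional review board.* That notice covers serious events. A withdrawal event managed in the facility is not serious under the plan's definition, so it could not trigger the notice.
- *That planned attrition caps the deaths missed.* The 10-15% attrition is a planning estimate that also covers surrogate withdrawal.
- *That weekly and 30-, 60- and 90-day follow-up exclude each other.* They can coexist; the documents do not say how.

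It is also fair to object that the *Data and Safety Monitoring Plan* and the design figures were not available, and that a drug may be restarted for reasons other than withdrawal. Both points stand and limit the verdict and the fix.

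**Conclusion.** The point holds in a limited form. One stated procedure applies a withdrawal-causality scale, and its scale sentence covers utilization only. Deaths outside hospice are judged without the scale being named. Hospice deaths probably do not enter the review. Withdrawal events managed in the facility have no stated route to adjudication.

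The entry rule can only lower the number of scale-adjudicated ADWEs or leave it unchanged. The size cannot be derived from the documents, the net tally could err in either direction, and no planned test changes. The conclusion assumes that the bracketed hospice example means what it appears to mean and that the unseen monitoring plan does not already close the gap. The matter is worth correcting because it decides which safety events are counted and the correction is cheap.

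**What to change.** 1. In the review section, name deaths in the scale sentence and put every death, hospice or not, through the same adjudication.
2. In the safety definitions, state that a suspected withdrawal event managed in the facility counts as an AE. During the abstraction already planned from nursing notes, incident reports and the medication administration record, flag an event when a drug on the final deprescribing list has been stopped or reduced and then either a note links a new or worse symptom to that change, or the record shows the drug restarted or increased. A restart triggers review; it does not prove withdrawal. Send only flagged events to the existing adjudicator, not every fall or behavioral episode.
3. Report ADWEs by route (utilization, death, facility-managed), and state which scale codes count as an ADWE.
4. Reconcile the weekly follow-up statement with the 30-, 60- and 90-day schedule. If weekly contact takes place, say what is recorded.

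If the *Data and Safety Monitoring Plan* already covers any of this, cite it in the safety section. If conduct is complete, as the past tense in *Study Setting* and *Interventions and Duration* suggests, apply items 1 to 3 retrospectively. Otherwise, report that ADWEs were ascertained only through utilization and unplanned death, and that the tally must not be read as a full count.

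The cost is one added abstraction item and a few more case reviews; the documents do not allow an estimate of how many. The reported AE count will rise, some hospice deaths may be codable only as doubtful or possible, and the flags depend on how fully staff charted symptoms.

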### Serious Adverse Events and Reporting Procedures

To ensure proper and timely reporting of adverse events, the following communication plan is utilized. The project coordinator is responsible for reporting adverse events to the safety officer and the IRB in a timely manner and in accordance with the IRB's guidelines. Our procedures are as follows:

1. IRB: PI will notify the IRB of any Serious, Unexpected, Study Related Adverse Event within 7 days of PI notification of the event. Any noncompliance with the IRB approved protocol that increases the risk or affects the patient's rights, safety, or welfare also need to be reported within one week. At the time of the IRB annual continuing review, the IRB receives copies of the reports prepared for the safety officer. Reports that identify a new risk or a change in the risk benefit ratio must be submitted to the IRB within 10 days of receipt by the PI.
2. Safety Officer: PI will notify the safety officer of any SAEs regardless of study-relatedness. Additionally, the safety officer will receive semi-annual reports summarizing all SAEs and AEs.

## Safety Officer

The SO will be the entity ultimately responsible for monitoring the safety of participants and the validity and integrity of the data. The SO is an experienced clinician-investigator with expertise in deprescribing and clinical interventions research and the clinical care of older persons with dementia in long-term care settings. The SO will maintain independence from the study and will not be involved in the conduct of the study or be a current collaborator of the PIs. The SO will be provided the study protocol and safety and data monitoring plan before study enrollment begins.

The safety officer is [name], Professor of Psychiatry, Pharmacology, and Medicine at Vanderbilt University Medical Center and Clinical Core Director of the Vanderbilt Alzheimer's Disease Research Center. [name] has expertise in clinical dementia care and dementia research. As described above, [name] is not part of the key personnel involved in this grant. He is qualified to review the patient safety data generated by this study because of his unique and extensive clinical and research expertise in clinical interventions in long-term care and dementia care settings. The research protocol, Data and Safety Monitoring Plan (DSMP), and informed consent documents will be submitted to the SO for approval prior to the beginning of the study.

The SO will review the entire IRB-approved study protocol regarding subject safety, the informed consent document regarding applicability and readability, and participant recruitment and retention milestones. Every six months, the study team will prepare safety reports to be reviewed by the SO for recommendations about modifications to the study. The report will include 1) a list of adverse and serious adverse events classified by severity and likelihood of being related to the study procedures; 2) whether adverse event rates are consistent with pre-study assumptions; 3) rates and reasons for study withdrawal; and 4) whether all participants met entry criteria. Summary reports of SO reports will be included in the annual NIH report for the project.

## STATISTICAL CONSIDERATIONS

### Sample Size & Attrition

Abe's Garden administration reported that all current residents lack decision-making capacity for healthcare decisions, and that all have surrogate decision makers. We estimate that the majority of the 41 residents/surrogates will participate in the study and conservatively estimate, based on investigators' work in previous studies in long term care, that attrition will be approximately 10-15%. We anticipate that some residents may die during the study and some surrogates may decline participation.

Power consideration: Given this is a pilot study, no formal power analysis will be conducted. But this pilot data would serve as a further guide for the power analysis for the following multi-center trial in preparation to test the clinical effectiveness of deprescribing among PWD in ALF care settings.

### Outcomes

Aim 1: Descriptive statistics (counts and proportions for categorical variables and means and SDs for continuous ones) will be used to describe Demographics at baseline, as well as Feasibility outcomes in Aim 1 at each measurement.

Aims 2 and 3: All statistical tests will be two-sided, with alpha = 0.05. For Aims 2 and 3, we will be applying a within-subjects intervention design to estimate the effect size of Shed-MEDS deprescribing intervention on Medication and Quality of Life outcomes. This design takes advantage of the smaller sample size in this pilot intervention, with each subject's 3-month retrospective review serving as their own control, which also removes the between-subjects differences in each condition. For the Medications outcomes in Aim 2 and the Quality of Life outcome of BPSD in Aim 3a, changes during the intervention period will be modeled using GEE, where time (multiple indicators), intervention group (one indicator) and their interaction will form the predictors, controlling

for baseline demographics. Hypothesized differences between the intervention and control groups will be examined using appropriate linear contrasts. For the DEMQoL-Proxy in Aim 3a, we will use a two-sample t-test to compare measurements at baseline with the 90-day follow-up, which is robust against normality or heterogeneity of variance.

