- Aim 3a: The Shed-MEDS intervention will not result in significant reductions in quality of life, as measured by Behavioral and Psychological Symptoms of Dementia (BPSD) events and DEMQOL-proxy scores at the end of 90 days.

**Potential for Impact:** The data from this study will inform feasibility and the implementation barriers and facilitators specific to PWD, their family proxies, and dementia care ALF staff. This information will inform tailored adaptations to the Shed-MEDS intervention in preparation for a multi-center R01 trial to test the clinical effectiveness of deprescribing among PWD in ALF care settings.

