## STUDY PROCEDURES

Data collection includes resident descriptive data as well as four groups of outcomes: medications, quality of life, safety, and feasibility. Table 1 shows a summary of the study timepoints along with the corresponding assessments. Upon enrollment, residents and their surrogate complete interviewer-administered questionnaires, which require approximately 30 minutes. Descriptive, medication, and safety data are obtained via records request from the ALF at enrollment and the three follow-up time points. Interviewer-administered questionnaires are conducted again 90-days after intervention ends. All interview assessments are completed by a trained research geriatric nurse practitioner.

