### Schedule of Assessments

**Table 1. Data Collection Schedule**

Measures	3-month Retrospective Review ∞	Enrollment	30- & 60-day Follow-up	90-day Follow-up
Demographics and Health Status				
Age, Gender, Race/Ethnicity, Education Level*		X		
Comorbidities*		X		
Cognitive Impairment (BIMS)	X*	X		X
Status: Long-Term Care, Hospice, Death*	X	X		X
Medications				
Total number of medications*	X	X	X	X
Sedative & Anticholinergic Drug Burden Index	X	X	X	X
Quality of Life				
DEMQoL-Proxy		X		X
BPSD*	X	X	X	X
Safety				
Falls*	X	X	X	X
Emergency Room Visits & Hospitalizations*	X	X	X	X
Feasibility				
RPATD (surrogate)		X		
Surrogate agreement w/ deprescribing recommendations		X	X	
Provider agreement w/ deprescribing recommendations		X	X	
Total number of conversations w/ prescribing MD/NPs		X	X	X
Total number of conversations with surrogates		X	X	X

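### The plan claims the 3-month look-back as each resident's own control for Aim 3, but DEMQOL-Proxy is never measured in that period, so its change is uncontrolled and is not an effect size of Shed-MEDS

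*Combined protocol and SAP*

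**What the plan says.** The Outcomes section of Statistical Considerations opens its account of the later aims with "For Aims 2 and 3, we will be applying a within-subjects intervention design to estimate the effect size" of the intervention on both medication and quality-of-life outcomes. The next sentence gives the comparator, "with each subject's 3-month retrospective review serving as their own control". Neither sentence excludes any outcome.

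Aim 3a names two quality-of-life measures, BPSD events and DEMQOL-Proxy, and predicts that the intervention "will not result in significant reductions in quality of life" at 90 days.

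The two measures are scheduled differently. In Table 1, BPSD is marked at the retrospective review, enrollment, 30 and 60 days, and 90 days. DEMQOL-Proxy is marked only at enrollment and 90 days. Study Procedures agrees: "Interviewer-administered questionnaires are conducted again 90-days after intervention ends", with no administration in between and none before enrollment.

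The Outcomes section then assigns the GEE model with its intervention-versus-control contrast to the medication outcomes and BPSD. For DEMQOL-Proxy it says "we will use a two-sample t-test to compare measurements at baseline with the 90-day follow-up".

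In Data Analyses, the repeated-measures paragraph lists Quality of Life among outcomes assessed at enrollment, 30, 60 and 90 days. The limitations paragraph says the within-subjects design was chosen to estimate effect sizes on medication and quality-of-life outcomes for later randomized trials. It also concedes that effects of time on the outcomes cannot be controlled.

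**The concern.** The own-control statement is the plan's justification for reading a single-arm change as an estimate of effect. For DEMQOL-Proxy that control does not exist: there is one value before the intervention and one after it. The general description of the design therefore gives this outcome a property that the schedule does not supply.

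Dementia is progressive, and proxy ratings can also shift for reasons unrelated to medication. A natural decline could be read as harm from deprescribing, and an upward shift in proxy ratings could hide harm. Avoiding worse quality of life is half of the overarching hypothesis, and Sample Size & Attrition says the pilot data will guide the power analysis of the multi-center trial. The practical risk is that an uncontrolled change is carried into that trial's planning as an intervention effect size.

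**Working it through.** The plan gives no effect size, SD or power for DEMQOL-Proxy, so there is no figure to reproduce. The check has two parts.

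**1. Claim against schedule**

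| Outcome | Look-back | Enrollment | 30/60 days | 90 days | Planned analysis |
|---|---|---|---|---|---|
| Medication count, DBI | yes | yes | yes | yes | GEE with control contrast |
| BPSD | yes | yes | yes | yes | GEE with control contrast |
| DEMQOL-Proxy | no | yes | no | yes | baseline vs 90 days |

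The own-control sentence can apply to the first two rows only. The four-time-point statement in Data Analyses fits BPSD but not DEMQOL-Proxy, which has two.

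**2. What the missing control does to the estimate**

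Let δ be the natural change over the interval and τ the effect of Shed-MEDS. With two measurements:

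E(90-day score − enrollment score) = δ + τ.

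One equation cannot separate two unknowns, so the bias for τ is exactly δ, whichever t-test is used. If a look-back value existed and drift were constant, subtracting the earlier change would give (δ + τ) − δ = τ. In simulations with no true effect, that contrast rejected in 4.6% to 5.4% of trials at every constant drift tried. Its standard error was √3 = 1.73 times larger. This shows what the claimed control would have provided.

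**Illustration of size.** Inputs from the documents: 40 residents, 10-15% attrition, two-sided alpha 0.05. Pairs: 40 × 0.90 = 36, or 40 × 0.85 = 34. Assumptions: natural decline of 2 or 4 points, SD of change 10 points (range 8 to 14), τ = 0.

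Paired test: noncentral t, n − 1 degrees of freedom, noncentrality δ/(SD/√n). With n = 36 and SD 10 this is 2/(10/6) = 1.2 and 4/(10/6) = 2.4.

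| Paired test | 2-point drift | 4-point drift |
|---|---|---|
| n = 36, SD 10 | 21.5% | 64.6% |
| n = 34, SD 10 | 20.5% | 62.0% |
| n = 36, SD 8 | 30.8% | 83.1% |
| n = 36, SD 14 | 13.3% | 38.5% |

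Planned two-sample test, by simulation, n = 36, SD of change 10. The cross-sectional SD is 10/√(2(1 − ρ)), where ρ is the assumed within-resident correlation. That is 10.0 at ρ = 0.5 and 12.9 at ρ = 0.7.

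| Two-sample test | 2-point drift | 4-point drift |
|---|---|---|
| ρ = 0.5 | about 6% | about 35% |
| ρ = 0.7 | about 1% | about 12% |

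The two-sample test rejects less often because it ignores the pairing. With no drift and no effect it rejects in under 1% of trials instead of 5%. This does not protect the estimate: the mean change is still off by the full 2 or 4 points.

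**The case against.** The strongest reply is that the Outcomes section, read to its end, already separates the outcomes. The model containing the control contrast is confined to the medication outcomes and BPSD, and DEMQOL-Proxy openly gets its own baseline-to-90-day comparison. A reader might infer that the plan conceals an uncontrolled analysis or intends a look-back analysis of data it will not have. It does neither. That part of the reply stands, and it makes this a fault of scope in one sentence. The own-control sentence is still never withdrawn for DEMQOL-Proxy, and the four-time-point statement repeats the impression that both Aim 3a measures have the same data.

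Second, the limitations paragraph already concedes time effects. It does so for all outcomes alike. It does not say that DEMQOL-Proxy lacks even the look-back that the others have, and the same paragraph presents the design as a way to estimate quality-of-life effect sizes.

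Third, Aim 3a claims no benefit, and decline from progression works against the sponsor's hypothesis. This is true of decline, but an upward shift in ratings works the other way.

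Fourth, a reader might take the 21% and 65% figures as the false-signal rates of this trial. They are not. They belong to a paired test, and the drift and SD are assumed. The planned test rejects far less often.

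**Conclusion.** The point holds as a minor overstatement affecting one secondary outcome of a pilot. The documents attribute a look-back control to the Aim 3 quality-of-life outcomes, and their own schedule shows that DEMQOL-Proxy does not have one. The bias equals whatever natural change occurs, in either direction. That conclusion needs no assumption about size; the rejection rates are illustrative only.

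Two stronger inferences are not supported. BPSD and the medication outcomes should not be called controlled comparisons on the strength of their look-back data: a preceding period is not a concurrent control, and the limitations paragraph says time effects remain. Nor can the 90-day BIMS score serve as a clean marker of progression. It is measured after the intervention, and the protocol itself links polypharmacy to cognitive decline and the targeted drug classes to delirium, so BIMS may respond to deprescribing.

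**What to change.** 1. In Outcomes, limit the own-control sentence to the medication outcomes and BPSD.
2. State there that DEMQOL-Proxy has no control period. Report it as the within-resident change from enrollment to the visit 90 days after the intervention ends, with a 95% CI, described as an uncontrolled change and not as an effect of Shed-MEDS. This replaces the two-sample comparison. With 36 pairs and the assumed SD of 10, the interval would be about ± 2.03 × 10/6 = 3.4 points. Because a paired interval detects drift more readily than the planned test, the label matters.
3. Word any Aim 3a conclusion on DEMQOL-Proxy to match, and do not carry its change forward as an intervention effect size.
4. In Data Analyses, correct the repeated-measures paragraph to match Table 1: DEMQOL-Proxy at two time points, BPSD at enrollment, 30, 60 and 90 days.

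The cost is protocol and SAP wording only, with no new data collection. A chart look-back cannot supply a past proxy interview, so none is asked for. The downside is a weaker stated claim for DEMQOL-Proxy.
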